8.3.2 Main Analysis of Primary Efficacy Endpoint

In each study Part, the primary efficacy endpoint of CFA (defined in Section 3.1) will be analyzed based on the Evaluable Set (ES-P1 and ES-P2 for study Part 1 and Part 2, respectively). The following methods will be used to address potential intercurrent events:

- Subjects with premature discontinuation of study drug in Part 1 or Part 2 or who did not receive any dose of study drug in both treatment periods for Part 1 or Part 2 will be excluded from ES-P1 or ES-P2, respectively
- Subjects without 100% of stool samples collected and analyzed by the laboratory in both treatment periods in Part 1 or Part 2 will be excluded from ES-P1 or ES-P2, respectively

The estimand corresponding to the primary efficacy endpoint for Part 1 is the mean CFA difference between Pancrelipase DR capsules MP and Creon® (pancrelipase) DR capsules among participants who complete both treatment periods and have 100% of stool

samples collected and analyzed by the laboratory in both treatment periods. The estimand corresponding to the primary efficacy endpoint for Part 2 is the mean CFA difference between Pancrelipase DR capsules AAPIS and Creon® (pancrelipase) DR capsules among participants who complete both treatment periods and have 100% of stool samples collected and analyzed by the laboratory in both treatment periods. The attributes of the estimands corresponding to the primary efficacy endpoint for each study Part are summarized in Table 2.

[figure not shown]
Table 2. Study M16-111 Estimand Attributes

Attributes of the Estimand					
Estimand	Population	Endpoint	Treatment	Handling of Intercurrent Events (IEs)	Population- Level Summary
Part 1 Primary	Evaluable set in Part 1 (CF subjects who are randomized and complete both treatment periods and have 100% of stool samples collected and analyzed by the laboratory in Part 1)	CFA at treatment Periods 1 and 2	Pancrelipase DR capsules MP or Creon® (pancrelipase) DR capsules	IE1: Premature discontinuation from either of the treatment periods in Part 1 IE2: Subjects without 100% stool sample collected in Part 1 Subjects with IE1 or IE2 will be excluded from the analysis population.	Mean CFA difference between two treatment groups
Part 2 Primary	Evaluable set in Part 2 (CF subjects who were randomized and completed both treatment periods and have 100% of stool samples collected and analyzed by the laboratory in Part 2)	CFA at treatment Periods 1 and 2	Pancrelipase DR capsules AAPIS or Creon® (pancrelipase) DR capsules	IE1: Premature discontinuation from either of the treatment periods in Part 2 IE2: Subjects without 100% stool sample collected in Part 2 Subjects with IE1 or IE2 will be excluded from the analysis population.	Mean CFA difference between two treatment groups

AAPIS = alternate active pharmaceutical ingredient site; CF = cystic fibrosis; CFA = coefficient of fat absorption; DB = double-blind; DR = delayed-release; IE = intercurrent event; MP = modernized process

8.3.3 Supplementary Analyses of the Primary Efficacy Endpoint

The following supplementary analysis of the primary efficacy endpoint will be conducted. In each study Part, the primary analysis will be repeated using all randomized subjects

(ITT-P1 and ITT-P2 for Part 1 and Part 2, respectively). In this analysis, subjects will be included using their observed CFA measurements from each available treatment period.

8.4 Secondary Efficacy Endpoint(s) and Analyses

8.4.1 Secondary Efficacy Analyses

[figure not shown]
The secondary efficacy endpoints will be the CNA, stool fat, and stool weight. These variables will also be analyzed separately using a mixed effects model including sequence, period and regimen as fixed effects and subjects within sequence as a random effect. From this model, an estimate of the treatment difference along with a 95% CI will be derived. All comparisons for all secondary variables between the regimen will be descriptive.

8.5 Additional Exploratory Efficacy Endpoint(s) and Analyses

8.5.1 Additional Exploratory Efficacy Analyses

The additional exploratory efficacy endpoints will be stool frequency, stool consistency, diarrhea, abdominal pain, bloating, and flatulence. Stool frequency will be summarized for the ITT Population by regimen for each diary day for Days 1-6 and by regimen for average stool frequency, which is calculated as the mean stool frequency for each subject of all non-missing diary days for Days 1-6. Stool consistency, diarrhea, abdominal pain, bloating and flatulence will be summarized (number and percentage for each ordinal category) for each diary day by regimen. Diary Days 1-6 will be included in the summary table. All comparisons for all additional exploratory variables between the regimen will be descriptive.

The EPI Symptom Diary, which collects assessments for the additional exploratory variables, was added as a case report form (CRF) as part of protocol amendment 6 (after many Part 1 subjects were already enrolled). Summary tables for the additional exploratory efficacy endpoints will only be provided for Part 1 if 6 or more subjects in the ITT Population complete at least one diary day in each treatment period of Part 1.

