5.6 Discussion and Justification of Study Design

5.6.1 Discussion of Study Design and Choice of Control Groups

The study Part 1 utilizes a cross-over as the optimal design to demonstrate non-inferiority for pancrelipase formulated as pancrelipase DR capsules MP 24,000 USP Units (lipase) as compared to Creon[®] (pancrelipase) Delayed Release capsules 24,000 USP Units (lipase). Each subject is able to serve as his/her own control, thus minimizing the number of subjects exposed to meet the primary objective.

The study Part 2 utilizes a cross-over as the optimal design to demonstrate non-inferiority for pancrelipase formulated as Pancrelipase DR capsules manufactured with AAPIS, 24,000 USP Units (Lipase) as compared to Creon[®] (pancrelipase) DR capsules 24,000 USP Units (lipase). Each subject is able to serve as his/her own control, thus minimizing the number of subjects exposed to meet the primary objective.

For both study Parts, due to the nature of the effects of pancrelipase on fat absorption, and the lack of absorption of pancrelipase, there is no concern related to any carry over effect with immediate rollover between DB Treatment Period 1 and DB Treatment Period 2. This interval is not intended as a washout period and any imbalance in this period length would not lead to any difference on study endpoints. The flexibility in the duration of the interval between the DB treatment period is intended to allow subjects to deal with logistical aspects (such as school and work schedules) related to the need for hospitalization/confinement during DB treatment, and to allow sites to more effectively manage their staffing and occupancy. The same applies to the interval between Parts, for subjects who elect to participate on both Parts.

The active control used in this study is commercially available Creon[®] (pancrelipase) Delayed Release capsules 24,000 USP Units (lipase) with previously demonstrated safety and efficacy.

DB treatment is chosen for this study to enhance scientific rigor in the study, and to eliminate any possibility of subjects biasing the results by altering diet consumption or stool collection during the study.

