4.0 Analysis Populations

The following population sets will be defined and used for the analyses for each study Part.

[figure not shown]
The Screening Confinement Set consists of all subjects who started screening confinement. The screening confinement period was removed from the study design in protocol amendment 6. Therefore, the Screening Confinement Set (denoted SC-P1) is only defined for Part 1 and includes subjects screened under protocol Amendment 5 or earlier.

The Intent-to-Treat (ITT) Population includes all randomized subjects in each study Part (denoted as ITT-P1 and ITT-P2 for Part 1 and Part 2, respectively). Subjects will be included in the analysis according to the treatment sequence to which they are randomized.

The Evaluable Set (ES) consists of all randomized subjects in each study Part who complete both double-blind (DB) treatment periods and have 100% of stool samples collected and analyzed by the laboratory and valid total fat intake value for both DB treatment periods. The ES for Part 1 and Part 2 will be denoted as ES-P1 and ES-P2, respectively. Subjects will be included in the analysis according to the study drug that they actually received.

The Safety Analysis Set consists of all randomized subjects who received at least 1 dose of study drug in the DB treatment periods in each study Part (denoted as SA-P1 and SA-P2 for Part 1 and Part 2, respectively). Subjects will be included in the analysis according to the regimen that they actually received.

The Open Label Safety Analysis Set in each study Part consists of all subjects who received at least 1 dose of open label Creon during any study period (denoted as OLSA-P1 and OLSA-P2 for Part 1 and Part 2, respectively). For Part 1, subjects who received open label Creon during the maintenance period (only applicable for subjects enrolled prior to protocol amendment 6) will also be included in OLSA-P1.

For Part 1, the population sets include: the Screening Confinement Set (SC-P1), Intent-to-Treat Population (ITT-P1), Evaluable Set (ES-P1), Safety Analysis Set (SA-P1) and Open Label Safety Analysis Set (OLSA-P1). For Part 2, the population sets include: the Intent-to-Treat Population (ITT-P2), Evaluable Set (ES-P2), Safety Analysis Set (SA-P2) and Open Label Safety Analysis Set (OLSA-P2).

[figure not shown]

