8.1 General Considerations

All efficacy analyses will be conducted for the Evaluable Set for study Part 1 and Part 2 using ES-P1 and ES-P2, respectively, unless otherwise specified. Efficacy analyses based on the EPI Symptom Diary will be conducted for the ITT Population for study Part 1 and Part 2 using ITT-P1 and ITT-P2, respectively.

The number of observations, mean, standard deviation, median, minimum and maximum will be summarized.

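### The exploratory diary endpoints are tabulated only by regimen on ITT, so one-period subjects can enter one column alone and no within-subject difference or its precision is reported

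*SAP*

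**What the plan says.** SAP 8.1 sets the population: "Efficacy analyses based on the EPI Symptom Diary will be conducted for the ITT Population for study Part 1 and Part 2". SAP 4.0 defines it: "The Intent-to-Treat (ITT) Population includes all randomized subjects in each study Part". SAP 8.2 adds that non-missing diary data are summarized without imputation.

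Within that population, SAP 8.5.1 has two layouts for stool frequency. One is daily: "Stool frequency will be summarized for the ITT Population by regimen for each diary day for Days 1-6". The other is "by regimen for average stool frequency, which is calculated as the mean stool frequency for each subject of all non-missing diary days", again over Days 1-6. Stool consistency, diarrhea, abdominal pain, bloating and flatulence are category counts and percentages by day and regimen. All of these comparisons are labelled descriptive. No paired difference, period or sequence breakdown, or model is specified for any diary item.

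For Part 1, where the diary form arrived with Amendment 6 after many subjects had enrolled, tables are produced only "if 6 or more subjects in the ITT Population complete at least one diary day in each treatment period of Part 1".

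Two other parts of the SAP treat the crossover differently. SAP 8.4.1 analyses CNA, stool fat and stool weight, also descriptively, with a "mixed effects model including sequence, period and regimen as fixed effects and subjects within sequence as a random effect" and a 95% CI. SAP 8.3.3 repeats the CFA model on ITT using each available period.

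**The concern.** Three features combine.

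- **The columns need not hold the same people.** ITT plus non-missing data admits subjects with a diary in one period only. They can arise from dropout (10-15% expected, SAP 2.4) or from the rule that incomplete stool collection bars the next confinement period (Protocol 5.4.1). In Part 1 they may also include subjects who were between periods when the diary was introduced. That last route is an inference, and no number is given. The six-subject condition decides whether the Part 1 tables appear. It does not limit who is in them.
- **No measure of the difference is given.** A reader who compares two columns of means and SDs can form only an independent-groups SE, which carries the full between-subject spread.
- **Period is not accounted for.** Subjects who leave after Period 1 add weight to Period 1 in whichever column they fall.

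The diary is the trial's structured daily symptom record completed by the subjects themselves. A modest symptom difference between products could be hard to see in these tables, or could partly reflect who kept a diary in which period.

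**Working it through.** **Is there a plan figure to reproduce?** Not for the diary: the documents state no SD, correlation, sample size or power for it. The nearest is CFA power in SAP 2.4, which rests on the SD of the within-subject difference. Using a noncentral t with N-2 df, SE = SD/√N, margin 12, one-sided alpha 0.005 and true difference 0:

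- N=22, SD 12: 95.7% (stated 96%)
- N=18, SD 10: 97.5% (stated 98%)

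These agree. They concern CFA and say nothing about the diary.

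**Precision.** Assumptions: SD 1 unit per period in each regimen, within-subject correlation ρ, and 18 complete pairs (the Part 2 evaluable target).

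- Independent-groups SE = √(2/18) = 0.333
- Paired SE = √(2(1-ρ)/18) = 0.333 × √(1-ρ)

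| ρ (assumed) | Paired SE | Smaller than 0.333 by |
|---|---|---|
| 0.4 | 0.258 | 23% |
| 0.6 | 0.211 | 37% |
| 0.8 | 0.149 | 55% |

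The percentage is 1-√(1-ρ), so it depends only on ρ.

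**What one-period subjects do to precision.** With n1 and n2 subjects in the columns and p of them paired, Var = 1/n1 + 1/n2 - 2ρp/(n1·n2). Take p=18, two extra subjects in one column, and ρ=0.6: 1/20 + 1/18 - 2(0.6)(18)/(20×18) = 0.0456, so SE = 0.213. This is almost the paired-only 0.211. The independent-groups SE is √(1/20 + 1/18) = 0.325. The actual variability hardly changes, but the table does not let a reader recover it.

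**What one-period subjects do to the column mean.** If k subjects sit in one column only, that mean moves by k/(p+k) of the gap between their level and that of the paired subjects.

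- Part 2 as planned (20 randomized, 18 completing), both one-period subjects in the same column: 2/20 = 10%
- Part 1 at the six-subject condition, k=2 assumed: 2/8 = 25%
- Part 1 at the six-subject condition, k=4 assumed: 4/10 = 40%

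**Day 1.** The diary is completed before the day's first dose (Protocol 5.3.1.1; Appendix C, table b, note g), and stool frequency looks back 24 hours (SAP 3.3). The Day 1 entry therefore precedes the period's treatment. If regimens differ by d on Days 2-6 and not at all on Day 1, the complete six-day average shows 5d/6, a loss of one sixth (about 17%).

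**The case against.** The strongest reply is that nothing here is an error. Protocol 8.1.2 plans descriptive summaries by treatment group for these variables, and the SAP does that. They are a third, exploratory tier, and a simpler analysis there than for secondary endpoints is ordinary practice. All of this stands.

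A reader might infer that the plan throws away the comparison the crossover was designed for. The documents do not support that. Protocol 5.6.1 does say "Each subject is able to serve as his/her own control", but the same sentence ties this to limiting the number of subjects exposed to meet the primary objective, which is CFA. Among subjects with both periods, the difference between column means also equals the mean within-subject difference. The contrast survives. Its precision, individual change, period adjustment and protection against a changing subject mix do not.

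A reader might also infer that an unpaired analysis is planned. It is not: SAP 8.5.1 specifies no SE, CI or test for the diary, so 0.333 is what a reader would derive from the columns.

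The mix effect may be small. Part 2 implies about two such subjects, and with 1:1 sequence randomization they can fall under either regimen. The Part 1 number is unknown, though its condition does secure at least six subjects with some diary data in each period.

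The descriptive label alone does not settle the matter. The secondary endpoints carry the same label and still receive the crossover model with an interval.

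**Conclusion.** The point holds as a low-cost improvement to an exploratory analysis. By-regimen tables on ITT with available data let one-period subjects into one column only, and they report no within-subject difference or its precision, although the SAP already contains a suitable model.

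The 23% to 55% reduction in SE is conditional on an assumed correlation of 0.4 to 0.8 with 18 pairs. It is not a figure from the documents. The possible shift in a column mean is 10% of the subject-level gap in the Part 2 worst case, and 25% to 40% in Part 1 under assumed counts.

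It would be wrong to read this as touching the trial's conclusions. Power, type I error and the non-inferiority decision rest on CFA, and the protocol and SAP agree on the diary plan.

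**What to change.** Amend SAP 8.5.1, before unblinding of the Part concerned, as follows.

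1. Keep the by-regimen tables.
2. Report, by regimen, how many subjects have diary data in both periods and how many in one only.
3. Analyse each subject's average stool frequency per period with the SAP 8.4.1 mixed model on ITT, using each available period, with a descriptive 95% CI. Exclude Day 1 from this average.
4. If pairs are few, as in Part 1 near six subjects (about 6-2 = 4 residual df), report the mean paired difference instead and state that it is not adjusted for period. Fix the cut-off in advance.
5. Optionally, for diarrhea, abdominal pain, bloating and flatulence, count subjects better, same or worse on test than on Creon among those with both periods, using a stated per-period summary without Day 1. This subset omits early leavers, so show it beside the ITT tables. Full category-by-category tables would be nearly empty at 6 to 18 pairs.
6. For stool consistency, use a defined binary such as any loose or watery day. Its categories (no movement, hard, formed, loose) do not run from best to worst, so a worst category is undefined.

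The cost is a small amount of extra programming in each Part, on data already collected. All results stay descriptive.

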5.3.1.1 Study Procedures

Informed Consent

At the Screening Visit, signed informed consent (and subject's assent as applicable) will be obtained from the subject before beginning any study-specific procedure. A prescreening consent may also be obtained from the subject prior to the screening visit so a stool sample can be collected and brought to the study site at the Screening Visit. Details on how informed consent/assent will be obtained and documented are provided in Section 9.3.

Subjects who have signed informed consent/assent and do not complete the study-specific procedures during the Screening Period will be considered screen failures. The reason(s) for screen failure will be documented in the source documents and will be captured in the eCRF.
Medical History

A complete medical history, including documentation of any clinically significant medical conditions and medications (including history of tobacco, nicotine-containing products and alcohol use) will be collected during the Screening Visit of the first part the subject is participating in. The Medical History form of the eCRF must contain all diseases/conditions for which the subject is taking concomitant medications.

For subjects who are participating in more than 1 study Part, the medical history will be reviewed at the screening visit for the next part the subject is participating in and updated for any new information available.

Pancreatic Enzyme Replacement Therapy (PERT)

Under the direction of their usual treating physician, at the screening visit subjects will start receiving open label Creon[®] at their usual established dose until all eligibility criteria are confirmed and the subject randomized, or until the subject is screen-failed.

For subjects who enter DB Treatment Period 2 directly from DB Treatment Period 1 (without leaving the hospital/confinement site): during the 24 h period until Treatment Period 2 can be started, subjects will be maintained at their usual diet and will be administered open label Creon[®] at the dose they received during the screening period. This daily dose of open label Creon[®] should be recorded in the eCRF.

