Food intake will be recorded by clinical site personnel on Day 3 (from first food intake), Day 4 and Day 5 (ending with last food intake). Although the timing of the stool collection in this protocol is noted as being 72 hours, individual subjects may experience different durations depending on their intestinal transit time.

Results of stool analyses during the DB Treatment Periods will be electronically transferred from the central laboratory to the study database using validated software.

The stools collected during the stool collection periods will be analyzed by a specialty lab contracted by AbbVie for the following:

• Stool Weight.

Total stool weight will be determined from the net weight of the stool samples collected.

• Stool Fat Content.

Stools will be analyzed by a central laboratory for fat according to the method of Van de Kamer⁵ to allow for the CFA determination.

• Stool Nitrogen Content.

Stools will be analyzed by a central laboratory for nitrogen according to the Kjeldahl⁶ method to allow for the CNA determination.*

* Stool nitrogen content will not be measured for the screening confinement period.

Patient EPI Symptom Diary

A paper EPI symptoms diary, which will collect information on stool frequency, stool consistency, diarrhea, abdominal pain, bloating and flatulence, will be provided to all subjects to complete on each day during each of the confinement periods. The EPI symptom diary should be completed before the subject receives the first study drug dose, prior to breakfast on each day. The clinical site personnel should remind subjects to complete the diary as instructed.

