For each study Part the 2 DB treatment periods will be separated by a maximum of 28 days, unless the subject elects to directly enter DB Treatment Period 2 from DB Treatment Period 1. In exceptional circumstances, such as impact by COVID-19-related activities, this period may be extended upon specific consultation with the sponsor.

At the end of DB Treatment Period 1 (between Visit 3 and Visit 4), the subjects will be given a 30 day supply of open label Creon[®] at the dose they received for the screening period to be taken during this period. In exceptional circumstances, such as impact by COVID-19-related activities, this period may be extended by an additional 30 days upon

specific consultation with the sponsor. If the subject elects to directly enter DB Treatment Period 2, the duration between Visit 3 and Visit 4 will be \leq 24 hours.

During the follow up period for both study parts, subjects will be given, at Visit 5, a supply of open label Creon[®] at the dose they received during the screening period to be taken during this period, along with their usual diet.

The study drug total daily dose, calculated based on the maximum dose of 4,000 LU/g of fat/day, as recommended in the current Creon[®] (Pancrelipase) delayed release capsules 24,000 USP Units (Lipase) label, will be administered orally, divided proportionally based on three meals and two snacks as follows:

Study diet g fat/day	# Capsules/ Meal	# Capsules/ Snack	Total # Capsules/Day	LU/Meal	LU/Snack	Total Daily Dose
100	4	2	16	96,000	48,000	384,000

For each of the treatment periods, the study drug intake will start on Treatment Period Day 1 at breakfast and will continue with each meal/snack until the last stool has been collected. Individual subjects may experience different treatment durations due to the fact the stool collection period depends on their intestinal transit time.

The study drug capsules must be swallowed intact (capsules must not be crushed, chewed or opened), and will be taken during the meal or snack (as per patient's usual practice), with enough fluids to swallow the capsules completely.

All scheduled doses must be taken. Subjects must be encouraged and instructed to consume all food provided as per the individualized diet during hospitalization/confinement.

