8.1.3 Safety Analysis

Safety analyses will be carried out using the Safety Analysis Set. Treatment-emergent AEs and SAEs, will be summarized and reported. Treatment-emergent AEs for DB Treatment Period 1 are defined as reported AEs that have a start date either on or after the first dose of the study drug during DB Treatment Period 1 and up to the end of DB Treatment Period 1. For DB Treatment Period 2, treatment emergent AEs are defined as reported AEs that have a start date either on or after the first dose of study drug during DB Treatment Period 2 and up to the end of DB Treatment Period 2. Adverse Events that occur during the administration of OL Creon[®] will be summarized separately for events that happen during the screening period and after randomization. The number and percent of subjects experiencing AEs will be tabulated by system organ class (SOC) and Medical Dictionary for Drug Regulatory Activities (MedDRA®) preferred term. In addition, summary of AEs by severity and relationship to study drug will be presented. Serious AEs, or AEs that lead to premature study discontinuation will be listed and described in detail. All these summaries will be done by treatment group. Mean change in vital signs and laboratory variables at each visit will be summarized. The last evaluation prior to the first dose of DB study drug in the corresponding treatment period will be used as baseline for the analysis in that treatment period. A frequency table will be presented for Potentially Clinically Important (PCI) vital sign findings. Shift tables for laboratory variables will be presented according to the reference ranges (low, normal or high).

Due to the small number of subjects per treatment group, only summary statistics will be applied to all the safety parameters.

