Concomitant Medication Review	X	X	Х	X	X	X ^a	
Adverse Events Review	X	X	X	X	X	X ^a	

a. Days 6, 7 or 8 depending on the appearance of the 1st blue dyed stool after the intake of the 2nd stool dye marker on Treatment Period Day 5 evening.

b. Until 2nd stool marker is passed on Day 6, 7 or 8.

c. Dietary record starts with Day 3 breakfast (1st meal following 1st stool dye marker intake on Day 2), and ends with Day 5 dinner or 2nd snack (last meal prior to 2nd stool dye marker intake on Day 5).

d. Stool collection starts after the subject passes the first stool dye marker (excluding the first blue dyed stool), and ends with the first blue dyed stool (including the blue dyed stool) after the second stool dye marker administration.

e. Study drug for the interval between Treatment Period 1 and Treatment Period 2 will be dispensed at discharge from confinement/hospitalization at Visit 3.

f. For the follow up period, the subject will be dispensed a supply of open label Creon[®], at the dose they received during the screening period, to be taken during the follow up period.

g. Completed prior to the administration of study drug, prior to breakfast on each day of study confinement.

h. Completed by the subject each day until subject is discharged.

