3.3 Additional Exploratory Endpoint(s)

To assess additional exploratory endpoints, subjects will complete an EPI Symptom Diary on a daily basis during each confinement treatment period. Additional exploratory efficacy endpoints include:

• Stool frequency

Stool frequency will be determined by self-report on the EPI Symptom Diary (number of bowel movements over the last 24 hours).

• Stool consistency

Stool consistency will be determined by self-report on the EPI Symptom Diary (No bowel movements over the last 24 hours, Hard/difficult to pass, Formed/normal, Loose/watery).

Diarrhea

Diarrhea will be determined by self-report on the EPI Symptom Diary (None, Mild, Moderate, Severe).

• Abdominal pain

Abdominal pain will be determined by self-report on the EPI Symptom Diary (None, Mild, Moderate, Severe).

Bloating

Bloating will be determined by self-report on the EPI Symptom Diary (None, Mild, Moderate, Severe).

[figure not shown]
• Flatulence

Flatulence will be determined by self-report on the EPI Symptom Diary (None, Mild, Moderate, Severe).

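### The by-regimen average stool frequency includes the Day 1 diary entry, which is made before the first blinded dose; with six entries, 1/6 of the average describes time before the regimen

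*SAP*

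**What the plan says.** SAP 8.5.1 summarises stool frequency by regimen in two ways: for each diary day from 1 to 6, and as a per-subject average "calculated as the mean stool frequency for each subject of all non-missing diary days for Days 1-6". The other diary items (stool consistency, diarrhea, abdominal pain, bloating, flatulence) are tabulated by day and are not averaged.

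Four other statements fix what the Day 1 entry measures:

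- **Recall window.** SAP 3.3 defines stool frequency as the "number of bowel movements over the last 24 hours".
- **Time of completion.** Protocol 5.3.1.1 states: "The EPI symptom diary should be completed before the subject receives the first study drug dose, prior to breakfast on each day". Footnote g to table b of Protocol Appendix C repeats it: "Completed prior to the administration of study drug, prior to breakfast on each day of study confinement". That table marks the diary on Day 1.
- **Start of blinded dosing.** Protocol 5.5.1 states that, in each period, "the study drug intake will start on Treatment Period Day 1 at breakfast".
- **Treatment before that.** Subjects take open-label Creon up to Day 1 of each period. Those who go straight into Period 2 take it "during the 24 h period until Treatment Period 2 can be started" (Protocol 5.3.1.1).

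On the analysis population, SAP 8.1 says: "Efficacy analyses based on the EPI Symptom Diary will be conducted for the ITT Population". No statement in either document drops the Day 1 diary entry, shifts it by a day or treats it as a baseline.

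**The concern.** An average labelled by regimen should describe time on that regimen. Here one of its six components is a pre-dose measurement. The Day 1 entry also reflects the usual diet and the subject's usual enzyme dose, whereas the blinded period brings the 100 g fat diet and a fixed 384,000 LU per day. It can therefore differ from the later entries for both regimens, including blinded Creon.

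There are two consequences. A real difference between regimens is diluted, so in a non-inferiority study this supportive symptom summary looks more alike across products than the on-treatment data are. In addition, a chance imbalance in pre-dose stool frequency leaks into the comparison in either direction. Because the diary is analysed in all randomised subjects, those who stop early stay in, and Day 1 weighs most for them.

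The protocol handles pre-dose values differently elsewhere. For vital signs and laboratory variables, Protocol 8.1.3 says: "The last evaluation prior to the first dose of DB study drug in the corresponding treatment period will be used as baseline".

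**Working it through.** The plan states no figure for this endpoint, so there is nothing to reproduce. The check is one of timing, followed by simple weights.

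**Step 1: what the Day 1 entry covers.** Each entry looks back 24 hours and is made before breakfast. The first blinded dose comes with Day 1 breakfast. The Day 1 window closes before that dose, so it holds zero hours on the regimen. Diary Days 2 to 6 cover the five 24-hour blocks that begin with Day 1 breakfast.

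**Step 2: alternative readings.**
- If diary Day 1 meant the first entry after dosing, six entries would run over the mornings of Days 2 to 7. Discharge can be on Day 6 (Protocol 5.1), so that reading does not fit a six-day table.
- If the protocol's phrase about the first dose means the first dose of each day, the Day 1 entry is still pre-dose.
- With direct entry into Period 2, Protocol 5.5.1 allows 24 hours or less between Visits 3 and 4. If the gap is shorter than 24 hours, part of the Day 1 window falls on the Period 1 blinded product, that is, the other regimen. It still contains no time on the Period 2 regimen.

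**Step 3: weight of Day 1.** Let k be the number of non-missing entries in Days 2-6, with Day 1 present.

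- Average = [1/(k+1)] × Day 1 value + [k/(k+1)] × mean of the later entries.
- Weight of Day 1 = 1/(k+1).
- Share of a constant on-treatment difference that is kept, if pre-dose levels are equal = k/(k+1).

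| k | Day 1 weight | Share of difference kept |
|---|---|---|
| 5 | 1/6 = 16.7% | 83.3% |
| 4 | 1/5 = 20% | 80% |
| 3 | 1/4 = 25% | 75% |
| 2 | 1/3 = 33.3% | 66.7% |
| 1 | 1/2 = 50% | 50% |
| 0 | 100% | 0% |

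**Step 4: illustrations (assumed values; the documents give none).**
- Dilution: on-treatment frequencies of 3 and 2 per day, pre-dose 2 per day in both periods. Days 1-6 give (2 + 5×3)/6 = 2.83 and (2 + 5×2)/6 = 2.00, a difference of 0.83. Days 2-6 give 3 − 2 = 1.00.
- Imbalance: a pre-dose difference of 0.5 stools per day shifts the six-entry average difference by 0.5/6 = 0.08, in either direction.

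**The case against.** The best case for leaving the rule alone is that little depends on it. The endpoint is exploratory and every comparison is descriptive. The by-day table shows Day 1 in its own row, so a reader can see the later days. In a crossover the same subject normally supplies both pre-dose values on the same open-label dose, so a large imbalance is unlikely. Subjects are confined and reminded to complete the diary, and expected dropout is 10-15%. The discontinuations tied to the dye markers fall at Day 5 or Day 8, by which time at least four later entries should exist, so a Day 1 weight of 17-20% is the realistic range. All of this stands as a limit on importance. The weights of 50% and 100% are arithmetic extremes.

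It can also be said that Days 2-6 are not purely on-treatment, since stools on the first blinded day may come from earlier meals. That is fair, and it means the 5/6 figure rests on the assumption of a constant difference. It is no reason to keep an entry that lies wholly before the regimen.

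Finally, the baseline rule in Protocol 8.1.3 concerns vital signs and laboratory values, and no change from baseline is planned for the diary. The two rules therefore do not conflict. The comparison only shows that the protocol recognises the pre-dose role of such values elsewhere.

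**Conclusion.** The concern holds and is minor. Followed as written, SAP 8.5.1 gives a by-regimen average in which the Day 1 entry, made entirely before the regimen starts, has weight 1/6 when all six entries are present and more when later ones are missing. The weights are exact. The reduction of the displayed difference to 5/6 assumes equal pre-dose levels and a constant on-treatment difference over Days 2-6. Without equal pre-dose levels the shift can go either way.

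In the by-day tables the only fault is that a pre-dose value appears under a regimen without saying so. The 24-hour recall is stated for stool frequency and, through one response option, for stool consistency. For the other symptoms the recall period is not given, but their Day 1 entry is still made before dosing. The primary analysis, the non-inferiority conclusion, type I error and sample size are unaffected in both Parts.

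**What to change.** In SAP 8.5.1, compute each subject's average stool frequency over non-missing diary Days 2-6. In all by-regimen diary tables, label Day 1 as the pre-dose value for that treatment period.

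An optional addition concerns the rule for printing the Part 1 diary tables, which asks for at least six subjects with one or more diary days in each treatment period. Day 1 entries alone could satisfy it. Requiring the diary day to fall within Days 2-6 closes that gap.

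The cost is one SAP sentence, one table label and, if adopted, one clause in the Part 1 display rule. Data collection does not change.
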